9.7.1.3 Safety evaluation

The safety (SAF) and open-label safety (OSAF) populations will be used as appropriate for summaries of the double-blind and open-label phases, respectively. Unless specified otherwise, comparison will be made to Baseline, which will be the measurement taken at Day 1 (Visit 2), or the sample obtained at an earlier visit (scheduled or unscheduled) which is closest to Day 1 if Day 1 measurement is missing.

9.7.1.3.1 Adverse Events

The number and percentage of patients reporting any adverse event during the double-blind treatment period and open-label phase will be summarized by primary system organ class, preferred term, and treatment (only for double-blind phase). Adverse events that are suspected to be related to study drug will be summarized. The maximum severity of all adverse events will be summarized. Serious adverse events and adverse events leading to study drug discontinuation (based on CRF AE data) will be summarized by primary system organ class, preferred term, and treatment (only for double-blind phase), and will be listed by patient.

In addition, all summaries will also be performed for the subgroups of CKD and non-CKD patients for double-blind phase and open-label phase, respectively.

9.7.1.3.2 Laboratory values

The details of lab parameters collected, SI units (note, only SI units will be reported), and normal ranges will be listed in CSR Section 16.

Table 2 Laboratory schedules by study protocol

Safety measurement	Visit
Standard hematology: Red blood cell count, hemoglobin, hematocrit, white blood cell count with differential (neutrophils, lymphocytes, monocytes, eosinophils, basophils), platelet count	Visits 1, 2, 5, 8, 9, 10 and 11

Safety measurement	Visit
Complete blood chemistry :	Visits 1, 2, 5, 8 and 11
Creatinine, non-fasting glucose, total bilirubin, AST/SGOT, ALT/SGPT, ALP, sodium, potassium, bicarbonate (total CO ₂), chloride, calcium, phosphorous, total protein, albumin, uric acid, cholesterol, triglycerides and eGFR	
Abbreviated blood chemistry:	Visits 9, and 10
Urea, creatinine, sodium, potassium, bicarbonate (total CO ₂) and eGFR	
Cystatin C GFR for CKD patients	Visits 2, 5, 10 and 11
Standard urinalysis: pH, specific gravity, glucose, protein, bilirubin, ketones, leukocytes, blood	Visits 1, 2, 5, and 11
Urinary albumin creatinine ratio (UACR) for CKD patients	Visits 2, 5, 10, and 11

Laboratory data will be summarized at baseline, endpoint of Period 1 (using LOCF) and endpoint of Period 2 (using LOCF) for absolute values and changes from baseline for each treatment. Baseline is defined as the last non-missing value prior to or at Week 0 (Visit 2). Laboratory shift tables are presented using normal ranges. In addition, the number and percentage of patients meeting pre-specified notable percentage change (see below) from baseline to any post-baseline result will be summarized. Separate listings are provided for hematology, blood chemistry, and urinalysis.

Pre-specified notable percentage changes for laboratory tests

Hematology

Erythrocyte count	>50% increase, >30% decrease
Hemoglobin	>50% increase, >30% decrease
Hematocrit	>50% increase, >30% decrease
Leukocyte count	>50% increase, >50% decrease
Platelet count	>75% increase, >50% decrease

Blood Chemistry

Albumin	>50% increase, >25% decrease
BUN	>50% increase
Creatinine	>50% increase
Glucose	>50% increase, >50% decrease

Total bilirubin	>100% increase
SGOT / AST	>150% increase
SGPT / ALT	>150% increase
Sodium	>5% decrease
Potassium	>20% increase, >20% decrease
Chloride	>10% increase, >10% decrease
Calcium	>10% increase, >10% decrease
Uric Acid	>50% increase
GFR (Schwartz)	>25% decrease

*Protocol stated that the laboratory variable is "urea". BUN (blood urea nitrogen) was reported in the study. Both urea and BUN were analyzed using the same analytical test and were identical when expressed in mmol/L.

Programming notes: the attached spreadsheet provides details regarding the parameters included in each laboratory relevant output.

CVAL489K2306
RAP M7 Irs repor

In addition, the number and percentage of patients meeting pre-specified selected notable absolute biochemistry values (see below) will be summarized.(Table 3) will be summarized.

Table 3 Pre-specified selected notable absolute values for laboratory tests

Laboratory Variables	Notable criteria
Total bilirubin	> 2 x upper limit of the reference range
SGOT	> 3 x upper limit of the reference range > 5 x upper limit of the reference range > 8 x upper limit of the reference range > 10 x upper limit of the reference range
SGPT	> 3 x upper limit of the reference range > 5 x upper limit of the reference range > 8 x upper limit of the reference range > 10 x upper limit of the reference range
Potassium	> 5.3 mEq/L > 5.5 mEq/L

	> 6.0 mEq/L
--	-------------

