1.2 Purpose

This study is part of the European Diovan® pediatric program and is conducted at the request of the EMA/Pediatric Committee (PDCO). Two previous trials, using valsartan, have been conducted in hypertensive children between 6 months and 5 years with mixed results. The EMA Committee for Medicinal Products for Human Use (CHMP) emphasized that a clinical need in this age group exists and that it would be relevant to conduct a new study ([Section 3.2](#)). The purpose of this study is to establish a dose response for valsartan solution in children 1-5 years old with hypertension (mean systolic blood pressure $\geq 95^{\text{th}}$ percentile), with or without chronic kidney disease (CKD). A sub-analysis will be performed to study the safety and tolerability of valsartan in children with CKD. An open-label phase has been added to study the safety of valsartan. The effects of valsartan on renal function and proteinuria will also be evaluated in CKD patients.

2 Study objectives

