3.6 Risks and benefits

As seen in previous pediatric trials using valsartan, the beneficial effects of valsartan in reducing blood pressure in children were confirmed both with short-term and long-term administration. Additionally, valsartan was well tolerated.

The VAL489K2306 trial is being conducted at the request of the EMA/PDCO, in order to assess the safety, tolerability and efficacy in children 1-5 years of age with hypertension, with or without CKD.

There are several direct and perceived benefits for children participating in this trial. Some of the benefits can be summarized as the following:

- Participation in this study will allow patients to receive medical attention by pediatric hypertension experts during the entire study duration. During screening, a thorough physical examination, detailed medical history, and complete laboratory tests will be performed for each potential patient. Some medical conditions may be detected early and get attention sooner due to the increased medical attention participation in this study.
- Study participation will also provide an opportunity for parents of the patients to discuss their children's medical conditions with these experts in great detail and formalize an individualized treatment plan for hypertension. During study participation, the patient and parent will have access to physicians and their medical teams to address any questions or concerns. The risk to patients will also be further minimized by complying with the study protocol and close clinical monitoring

Some of the risks associated with this trial include:

- Hyperkalemia: Hyperkalemia is a known and identified risk with drugs that interfere with the renin-angiotensin system especially in patients with concomitant renal disease. Since at least 50% of patients enrolled in this trial will have CKD, it is likely that some will experience hyperkalemia. To ensure their safety, patients with a serum potassium level > 5.3 mmol/L during the trial will need to repeat the laboratory test (advisable within one week after results were sent). All patients with serum potassium > 5.3 mmol/L should be followed and appropriate medical care given. If the repeat value confirms serum potassium > 5.5 mmol/L, the patient must be immediately discontinued from the study and the appropriate medical care given.

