Study drug start date in Period 2 is Visit 5 date. Last study drug date in Period 2 is the last known study drug date from the study completion panel.

Start and end dates for individual doses will be used to calculate duration of exposure by dose. For each dose, duration of total exposure to each specific dose will be derived accordingly.

In addition, duration (in days) of exposure to study drug during the entire study (with Period 1 and Period 2 together) will be summarized similarly by dose and overall (including all doses) for SAF.

Prior and concomitant antihypertensive medications taken during the study will be summarized by treatment for the following 3 periods separately: prior to taking study medication by double-blind treatment in SAF, double-blind treatment period 1 by treatment in SAF and open-level period 2 in OSAF. Concomitant non-antihypertensive medications and significant non-drug therapies during the study will be summarized for (i) prior to study drug and (ii) after study drug.

The same summaries as above will be performed for the subgroups of CKD and non-CKD patients.

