In addition to the primary analysis based on the FAS population, a similar analysis for the primary endpoint will also be performed on the PPS population as a supplementary assessment.

To further assess the dose response, the change from baseline at Week 6 endpoint in MSBP will be analyzed in FAS by an analysis of covariance model with CKD strata as the factor and baseline MSBP as a covariate, and dose per body weight (mg/kg) as the main regressor. The estimated slope with 95% confidence interval and p-value for the dose per body weight will be provided.

Subgroup analysis for CKD/non CKD patients

Similar analysis of the primary efficacy variable for the treatment comparison will be performed for the subgroup of CKD patients and for the subgroup of non-CKD patients (per CKD yes/no strata). The estimated treatment difference, 95% confidence interval and two-sided p-value for the treatment comparison within each subgroup analysis will be provided. Furthermore, treatment-by-CKD strata interaction in the entire FAS will be assessed by inclusion of the additional interaction term to the primary analysis model for the overall analysis in FAS and the p-value for the respective interaction term will be provided.

Descriptive statistics

The change from baseline in MSBP (together with the corresponding baseline and post-baseline MSBP) during double-blind phase will be summarized by treatment and visit (including Week 6 LOCF endpoint) for the FAS (for overall as well as for each of the CKD/non-CKD subgroup). The MSBP will be plotted versus visit (not including Week 6 LOCF endpoint) by treatment group for the FAS (for overall as well as for each of CKD/non-CKD subgroup). In addition, change from baseline in MSBP will also be plotted versus visit by treatment group for the FAS (for overall as well as for each of CKD/non-CKD subgroup).

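### The SAP states no CKD split for its laboratory tables, so potassium, creatinine and Schwartz eGFR abnormalities in children with CKD are pooled with the rest

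*SAP*

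**What the plan says.** Protocol 1.2 commits to a CKD safety analysis: "A sub-analysis will be performed to study the safety and tolerability of valsartan in children with CKD". Protocol 2.2 lists safety with or without CKD, and eGFR in the CKD subset, as secondary objectives. Protocol 3.6 describes hyperkalemia as a known risk of drugs acting on the renin-angiotensin system, more so with renal disease, and adds: "Since at least 50% of patients enrolled in this trial will have CKD, it is likely that some will experience hyperkalemia".

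The SAP states the CKD split section by section:

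- **9.7.1.1**, after exposure and concomitant medication: "The same summaries as above will be performed for the subgroups of CKD and non-CKD patients".
- **9.7.1.2.1**, for blood pressure summaries: "for overall as well as for each of the CKD/non-CKD subgroup". Similar wording follows for the responder analyses and for Period 2.
- **9.7.1.3.1**, closing the adverse event text: "all summaries will also be performed for the subgroups of CKD and non-CKD patients for double-blind phase and open-label phase, respectively".

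Section 9.7.1.3.2 has no such sentence. It opens with "Laboratory data will be summarized at baseline, endpoint of Period 1 (using LOCF) and endpoint of Period 2 (using LOCF) for absolute values". Changes are handled alike, and the only grouping given is by treatment. It then lists shift tables, counts of notable percentage changes (among them potassium, creatinine and a Schwartz GFR decrease above 25%) and Table 3, for which "the number and percentage of patients meeting pre-specified selected notable absolute biochemistry values (see below) will be summarized". Table 3 includes potassium above 5.3, 5.5 and 6.0. No grouping is stated for the shift tables or the counts.

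**The concern.** The laboratory tables are where hyperkalemia is measured. They are also the main safety tables for which no CKD breakdown is stated. Followed as written, the plan would report one potassium rate per arm over a mixed population, although the protocol expects the risk to be concentrated in one part of it. A reader of the study report could not recover from the summary tables how many CKD children crossed a potassium threshold, or whether this differed by dose among them. The same holds for creatinine increases and for the count of notable Schwartz GFR decreases. For these parameters the promised CKD safety sub-analysis would not be delivered.

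**Working it through.** **1. Which CKD-specific outputs are stated**

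| Output | CKD-specific version in the SAP? | Section |
|---|---|---|
| Exposure, concomitant medication | Yes | 9.7.1.1 |
| MSBP, MDBP, responders | Yes | 9.7.1.2 |
| Adverse events | Yes | 9.7.1.3.1 |
| UACR, cystatin C GFR | Yes, CKD children only | 9.7.1.2.2 |
| Potassium, creatinine, Schwartz eGFR: values, changes, shifts | Not stated | 9.7.1.3.2 |
| Notable percentage changes | Not stated | 9.7.1.3.2 |
| Table 3 potassium thresholds | Not stated | 9.7.1.3.2 |

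Cystatin C is drawn at Visits 2, 5, 10 and 11. Schwartz eGFR is also available at Visits 8 and 9 (SAP Table 2), and it carries the only planned count of notable GFR decline.

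**2. Size of the CKD subgroup**

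Protocol 6.2 requires at least 50% CKD and stops non-CKD enrolment at 65. With 130 randomised, 0.50 × 130 = 65, which reproduces the cap. So at full enrolment there are at least 65 CKD children, about 32 or 33 per arm under 1:1 allocation stratified by CKD. If the 116 expected to enter Period 2 keep that share, 0.50 × 116 = 58 have CKD.

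**3. Dilution by pooling (assumed rates; the documents give none)**

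With CKD share s, pooled rate = s × p(CKD) + (1 − s) × p(non-CKD). For potassium above 5.5:

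| s | p(CKD) | p(non-CKD) | Pooled | CKD ÷ pooled |
|---|---|---|---|---|
| 0.5 | 10% | 2% | 6.0% | 1.67 |
| 0.5 | 15% | 2% | 8.5% | 1.76 |
| 0.5 | 20% | 5% | 12.5% | 1.60 |
| 0.7 | 10% | 2% | 7.6% | 1.32 |
| 0.7 | 15% | 2% | 11.1% | 1.35 |
| 0.7 | 20% | 5% | 15.5% | 1.29 |

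First row: 0.5 × 10% + 0.5 × 2% = 6.0%, and 10 ÷ 6.0 = 1.67.

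**4. Dilution of a dose difference**

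If the difference between arms exists only in CKD children, the pooled difference is s times the CKD difference. An assumed 15 points becomes 0.5 × 15 = 7.5 points at a 50% share and 0.7 × 15 = 10.5 points at 70%.

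**5. What a split table could resolve**

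With 33 CKD children per arm and assumed rates of 15% and 5%, the standard error of the difference is √(0.15 × 0.85/33 + 0.05 × 0.95/33) = 0.073. The 95% interval is 10 ± 14 points, roughly −4 to +24. Split tables would therefore describe the data rather than test a dose effect.

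**The case against.** **The adverse event split may already do the work.** Protocol 7.1 counts a laboratory abnormality as an adverse event if it causes signs or symptoms, is considered clinically significant or needs therapy. Protocol 5.5.9 calls for a repeat test and follow-up above 5.3 mmol/L and for discontinuation when a repeat confirms a value above 5.5. Many important cases may therefore reach adverse event tables that are split by CKD. This narrows the gap but does not close it: an asymptomatic value above a threshold need not become an adverse event.

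**The all-summaries sentence could extend to all safety data.** The sentence ends the adverse event subsection, before the laboratory subsection begins, and the SAP repeats the split where it wants it. The natural reading is adverse events only.

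**An unseen attachment might specify subgroups.** The SAP cites a spreadsheet for the laboratory outputs, which is not available here. It is described as listing parameters per output, with no mention of subgroups. The supportable statement is that no split is stated, not that none was ever intended.

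**The SAP follows protocol 9.5.3**, which also summarises laboratory data by treatment without mentioning CKD. That is so, but it leaves the commitment in protocol 1.2 unmet.

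**Stronger readings that the documents do not support.** A reader might infer that renal function in CKD children is wholly averaged away. It is not: SAP 9.7.1.2.2 analyses cystatin C GFR in CKD children alone, by ANCOVA between doses in Period 1 and by visit in Period 2, and UACR likewise. A reader might take eGFR decline to be the risk that protocol 3.6 names. That section names hyperkalemia. A reader might also infer that pooling halves the CKD rate or hides the dose contrast. Halving needs a zero non-CKD rate at exactly 50% CKD, which is the minimum share. The relative contrast may survive: with assumed CKD rates of 15% and 5%, a 1% non-CKD rate, and 33 CKD and 32 non-CKD children per arm, the pooled rates are (33 × 0.15 + 32 × 0.01)/65 = 8.1% and (33 × 0.05 + 32 × 0.01)/65 = 3.0%. That ratio is 2.7, against 3.0 within CKD.

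**Conclusion.** The point holds for potassium, creatinine and Schwartz eGFR. No CKD version of their laboratory tables is stated, so the CKD safety sub-analysis in protocol 1.2 is only partly delivered. The argument from a named risk applies to potassium. For GFR the gap is limited to the Schwartz values and their notable-decrease count.

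The size is illustrative. On the assumed rates, the CKD rate is about 1.6-1.8 times the pooled rate at 50% CKD and about 1.3 times at 70%. An absolute dose difference confined to CKD children is halved at 50%. The direction needs only that CKD children are at higher risk, as protocol 3.6 expects. The factor depends on the actual CKD share and on rates that the documents do not give. This is a reporting gap in safety; it does not touch the primary analysis.

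**What to change.** In SAP 9.7.1.3.2, add CKD and non-CKD versions of the change-from-baseline, shift, notable percentage change and Table 3 summaries, for at least potassium, creatinine and Schwartz eGFR (of these, Table 3 covers potassium only):

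- **Period 1 (SAF):** by dose arm within CKD and within non-CKD.
- **Period 2 (OSAF):** by CKD status.

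Label them as descriptive. The argument does not require CKD versions of the hematology or liver tables, nor confidence intervals that the SAP does not give for laboratory counts elsewhere.

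The cost is a sentence or two of SAP text and repeat runs of planned tables. CKD status is already the randomisation stratum and an established subgroup, so no new data are needed. The downside is more tables with small cells: with about 33 CKD children per arm, even zero events would leave a one-sided 95% upper bound of 1 − 0.05^(1/33) = 8.7%.

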9.7.1.3.3 Vital signs and other safety assessments

The change from baseline in pulse, height, body weight, and head circumference will be summarized by treatment (only for double-blind phase) and visit for both periods.

The number of subjects with or without clinically significant ECG abnormalities at each ECG assessment will be tabulated.

The taste assessment will also be summarized on SAF.

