Title	A 6 week, randomized, multicenter, double-blind, double-dummy study to evaluate the dose response of valsartan on blood pressure reduction in children 1-5 years old with hypertension, with or without chronic kidney disease, followed by a 20 week open-label titration phase
Brief title	Dose response study of valsartan in children (1-5 years) with hypertension, with or without chronic kidney disease
Sponsor and Clinical Phase	Novartis
Investigation type	
• VAL489 (Valsartan) 0.25 mg/kg or 4 mg/kg and matching placebo• VAL489 (Valsartan) 4 mg/kg
Study type	Interventional
Purpose and rationale	This study is part of the European Diovan® pediatric program and is conducted at the request of the EMA/Pediatric Committee (PDCO). Two previous trials, using valsartan, have been conducted in hypertensive children between 6 months and 5 years with mixed results. The EMA Committee for Medicinal Products for Human Use (CHMP) emphasized that a clinical need in this age group exists and that it would be relevant to conduct a new study (Section 3.2). The purpose of this study is to establish a dose response for valsartan solution in children 1-5 years old with hypertension (mean systolic blood pressure \geq 95 th percentile), with or without chronic kidney disease (CKD). A sub-analysis will be performed to study the safety and tolerability of valsartan in children with CKD. An open-label phase has been added to study the safety of valsartan. The effects of valsartan on renal function and proteinuria will also be evaluated in CKD patients.
Primary Objective(s) and Key Secondary Objective	
Primary:
 
• To evaluate if a dose dependent reduction in mean systolic blood pressure (MSBP) exists when comparing two doses of valsartan solution (0.25 mg/kg and 4 mg/kg) over a 6 week period in children 1-5 years old with hypertension (MSBP \geq 95th percentile for age, gender and height), with or without CKD. 
Secondary:
 
• To assess the efficacy of valsartan in reducing the mean diastolic blood pressure (MDBP) in children with hypertension.• To assess the efficacy of valsartan in controlling the MSBP and MDBP in children with hypertension. The target mean BP is <90th percentile for age, gender and height.• To assess the safety and tolerability profile of valsartan in children with

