- Study drug solution contains sucrose (0.3 g per milliliter) which should be taken into account in diabetic patients because it may increase blood sugar levels; methyl parahydroxybenzoate which may cause an allergic reaction (possibly delayed), and poloxamer (188) which may cause softened stools.
- Liver function monitoring:
For patients with any clinically relevant degree of LFT elevation (AST/ALT/total bilirubin), frequent monitoring will be performed until the values approach either normal range or baseline values. For patients with LFT elevation of $> 3 \times$ ULN, a hepatitis panel test (A, B, C, D, E) will be requested and a retest will be done for the LFT and to rule out viral hepatitis. If the retest shows that the LFT elevation is still $> 3 \times$ ULN, then the patient must be discontinued from the study immediately. If the retest shows that the LFT elevation is less than or equal to $3 \times$ ULN, the patient may remain in the study, if considered medically safe to do so by the investigator.
- Hypotension: Hypotension is an identified risk in certain patients and is an extension of the pharmacologic effect. Dizziness, vertigo, and syncope may be related to low blood pressure, but may also be associated with other conditions. The protocol has specific detailed procedures for careful blood pressure monitoring at each visit. The protocol has defined stopping rules for study medication or study discontinuation based on blood pressure measurements.
- As in any clinical study, there are always unknown risks and new side effects that are not now known could also occur.

The results from this trial will provide further information on the efficacy, safety, and tolerability of valsartan in hypertensive pediatric patients with or without CKD.

4 Population

The study population will consist of a representative group of 130, male and female children age 1-5 years by visit 2. All patients must have a history of hypertension defined as a MSBP $\geq 95^{\text{th}}$ percentile to be eligible for randomization into this study. Approximately 50 sites are planned for this study. A total of 200 patients will be screened to randomize 130 patients with an anticipated screen failure rate of 35%. A drop out rate of 10% during the double-blind period is expected. A total of 116 patients are expected to complete the double-blind period and enter the open-label period. Patients will be stratified based on CKD status (yes /no).

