6.5.3 Height, weight, and head circumference

Height in centimeters (cm), body weight (to the nearest 0.1 kilogram [kg] in indoor clothing, but without shoes), and head circumference will be measured.

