9.5.3 Safety variables

The assessment of safety will be based mainly on the frequency of adverse events and on the summary of laboratory values for the safety populations. Other safety data (e.g. weight, height, resting pulse and head circumference) will be summarized as appropriate. The safety (SAF) and open-label safety (OSAF) populations will be used as appropriate for summaries of the double-blind and open-label periods.

Adverse events newly occurring or worsening during the double-blind treatment period and open-label period will be summarized by primary system organ class, preferred term, and treatment (only for double-blind period). Suspected study-drug related adverse events will be summarized similarly.

Serious adverse events and adverse events leading to study drug discontinuation (based on CRF AE data) will be summarized by primary system organ class, preferred term, and treatment, and will be listed by patient.

Laboratory data will be summarized by treatment for change from baseline and for occurrence of abnormality as appropriate.

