Appendix 2: Pediatric blood pressure tables and growth charts

Blood pressure percentiles will be determined with the below BP tables which were published by the *National High Blood Pressure Education Program Working Group on High Blood Pressure in Children and Adolescents* ([NHBPEP Fourth Report 2004, Lurbe 2009](#)).

Height percentiles will be determined with below growth charts published by *Centers for Chronic Disease Control and Prevention* (<http://www.cdc.gov/growthcharts>).

Using the tables

Use the correct gender growth chart to determine the height percentile.

Measure and record the child's MSBP and MDBP.

Use the correct gender table for SBP and DBP.

Find the child's age on the left side of the table. Follow the age row horizontally across the table to the intersection of the line for the height percentile (vertical column).

There, find the 50th and 95th percentiles or values for 20% and 25% above 95th percentile for SBP in the left columns and for DBP in the right columns.

[figure not shown]
Special methods and scales

Birth to 36 months: Girls

Length-for-age and Weight-for-age percentiles

NAME _____

RECORD # _____

Published May 30, 2000 (modified 4/20/01)

SOURCE: Developed by the National Center for Health Statistics in collaboration with the National Center for Chronic Disease Prevention and Health Promotion (2000). <http://www.cdc.gov/growthcharts>

[figure not shown]
SAFER • HEALTHIER • PEOPLE™

2 to 20 years: Girls

Stature-for-age and Weight-for-age percentiles

NAME _____

RECORD # _____

Published May 30, 2000 (modified 11/21/00).

SOURCE: Developed by the National Center for Health Statistics in collaboration with
the National Center for Chronic Disease Prevention and Health Promotion (2000).
<http://www.cdc.gov/growthcharts>

[figure not shown]

SAFER • HEALTHIER • PEOPLE™

Birth to 36 months: Boys Length-for-age and Weight-for-age percentiles

NAME _____

BECOBD # _____

Published May 30, 2000 (modified 4/20/01).

[figure not shown]
SOURCE: Developed by the National Center for Health Statistics in collaboration with the National Center for Chronic Disease Prevention and Health Promotion (2000). <http://www.cdc.gov/growthcharts>

SAFER • HEALTHIER • PEOPLE™

2 to 20 years: Boys
Stature-for-age and Weight-for-age percentiles

NAME _____
RECORD # _____

Published May 30, 2000 (modified 11/21/00).

SOURCE: Developed by the National Center for Health Statistics in collaboration with

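### After Week 6 growth is summarised only as raw change from baseline in one open-label group; an age- and sex-standardised summary is needed to recognise a moderate slowing

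*SAP*

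**What the plan says.** The SAP's plan for growth is one sentence in 9.7.1.3.3: "The change from baseline in pulse, height, body weight, and head circumference will be summarized by treatment (only for double-blind phase"). The same sentence asks for results at each visit of either period. Under SAP 9.7.1.3 the baseline for safety data is "which will be the measurement taken at Day 1 (Visit 2"), so the last open-label change spans about 26 weeks.

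Protocol 9.5.3 names no metric: "Other safety data (e.g. weight, height, resting pulse and head circumference) will be summarized as appropriate". Protocol 6.5.3 fixes the units: "Height in centimeters (cm), body weight (to the nearest 0.1 kilogram [kg] in indoor clothing, but without shoes), and head circumference will be measured".

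The population is "male and female children age 1-5 years by visit 2" (Protocol section 4). The title describes a 6-week randomised comparison "followed by a 20 week open-label titration phase", and Protocol 3.1 moves all patients into that phase at Visit 5.

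A growth reference is already in the protocol, for another purpose. Appendix 2 says "Height percentiles will be determined with below growth charts published by" the CDC, so that the blood pressure tables can be read. Its charts cover length-for-age and weight-for-age from birth to 36 months, and stature-for-age and weight-for-age from 2 to 20 years, separately for girls and boys.

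Neither document plans a z-score, a growth percentile, a growth velocity, an age band or a notable-change threshold for growth.

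**The concern.** Healthy children of these ages grow, and younger ones grow faster. A mean gain in height or weight is therefore expected whether or not growth has slowed. It can be interpreted only against what children of that age and sex would have gained. A concurrent control arm could supply that comparison, but Period 2 has none. An external reference is the remaining option, and the plan does not use one.

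The open-label phase was added to study safety (Protocol 1.2). The longer duration was chosen partly to assess safety in hypertensive children with CKD (Protocol 3.3), who are to make up at least half of enrolment. What is at stake is whether measurements already being collected can say anything about growth over 26 weeks.

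**Working it through.** The documents give no growth figure, so there is none to reproduce. The check has three parts.

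**1. What is available after Week 6**

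- Metric: change from Visit 2 in measured units (SAP 9.7.1.3.3; Protocol 6.5.3).
- Comparator: none. All children take open-label valsartan (Protocol 3.1), and the summary is not split by treatment.
- Data needed to standardise: date of birth, sex, height and weight are collected (Protocol 6.2), and the CDC charts are named (Appendix 2).

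**2. Why raw gain does not identify slowed growth**

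Annual height gains of 5 to 12 cm are an assumption; the documents give no growth rates. Gain over w weeks = annual gain × w/52. With a 20% slowing throughout, the 26-week gain is multiplied by 0.8.

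| Assumed annual gain (cm) | 6-week gain (cm) | 26-week gain (cm) | 26-week gain, 20% slower (cm) |
|---|---|---|---|
| 5 | 0.58 | 2.5 | 2.0 |
| 7 | 0.81 | 3.5 | 2.8 |
| 10 | 1.15 | 5.0 | 4.0 |
| 12 | 1.38 | 6.0 | 4.8 |

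Every slowed figure is still a clear gain. A mean of 4.0 cm fits unslowed growth at 8 cm a year (8 × 26/52 = 4.0). It also fits growth at 10 cm a year slowed by 20% (10 × 26/52 × 0.8 = 4.0). Raw change alone cannot separate the two. Change in a z-score can, because a child who stays on the same centile has a change of zero and one who falls behind has a negative change.

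**3. Whether the 6-week summary by dose fills the gap**

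- Inputs: 116 completers (SAP 9.7.2) randomised 1:1, so 58 per arm; two-sided 0.05 and 80% power, borrowed from the primary endpoint as a yardstick.
- Detectable difference = (1.960 + 0.842) × √(2/58) = 0.52 SD.
- With an assumed SD of 0.5 to 1.0 cm for 6-week height change, this is 0.26 to 0.52 cm.
- As a share of the 6-week gain: 0.26/1.38 = 19% at best and 0.52/0.58 = 90% at worst.

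Both arms receive valsartan, so an effect common to both doses would cancel. The contrast is useful, but it does not address growth to 26 weeks.

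**The case against.** The strongest case against is that growth is not an objective. Protocol 2.2 lists general safety and tolerability. Protocol 9.5.3 rests safety mainly on adverse events and laboratory values and places height, weight and head circumference among other safety data. Protocol 3.2 justifies the 26 weeks by proteinuria. How an ancillary descriptive variable is displayed is partly a matter of preference. This stands, and it limits the weight of the point.

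There is also a partial safeguard. Significant examination findings after the start of study drug must be reported as adverse events (Protocol 6.5.1), and adverse events are summarised by CKD status in both phases (SAP 9.7.1.3.1). That route catches a problem an investigator notices in one child, but not a modest shift in the group.

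Four stronger readings are tempting, and the documents do not support them:

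- *Growth is summarised only in a single uncontrolled arm.* The first 6 weeks are summarised by randomised dose.
- *No growth effect of any kind could be seen.* A gross effect such as weight loss would show in the raw change.
- *The spread of ages hides the shift.* Spread between children does not conceal a shift in the mean. If 26-week gains were uniform over an assumed 3 to 6 cm, the SD would be 3/√12 = 0.87 cm and the standard error with 116 children 0.87/√116 = 0.08 cm. The mean would be precise; what is missing is the value to compare it with. Nor do the documents give an open-label dropout rate from which to size a change in age mix, since their 10% is for the double-blind period.
- *A fall in z-score would show harm from valsartan.* At least half the children have CKD, renal transplant recipients may enrol (Protocol 4.2) and stable chronic steroids are permitted (Protocol 5.5.8). Any of these can move z-scores, and Period 2 has no control.

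**Conclusion.** The point holds for the period after Week 6. Raw change from Visit 2 in one open-label group, with no age- and sex-specific reference, cannot reveal a moderate slowing of growth in children aged 1 to 5, and the 6-week comparison of two active doses does not make up for this. The structural part rests on the text of the two documents. The size (a 20% slowing still showing as a gain of 2.0 to 4.8 cm) rests on assumed growth rates of 5 to 12 cm a year and is an illustration only.

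This is a minor, inexpensive improvement to safety reporting. The primary analysis is untouched, and no stated objective fails because of it. A reader might infer that standardised values would settle whether valsartan affects growth. They would not: they would make the open-label data interpretable against a reference, but would not attribute a cause.

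**What to change.** In SAP 9.7.1.3.3:

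- Derive height-for-age and weight-for-age z-scores, or percentiles, from the CDC reference named in Protocol Appendix 2.
- State which chart applies at 24 to 36 months, where the two sets overlap, and how a child who crosses between them is handled. Protocol 6.5.3 does not say whether height is taken lying or standing, so the rule should cover that too.
- Summarise change from Visit 2 in these measures at each visit where they are taken: by dose in Period 1, overall in Period 2, and split by CKD status.
- Keep the raw summaries.
- Summarise head circumference by one-year age band, since no chart title in Appendix 2 covers it.
- State that the Period 2 results are descriptive, because CKD, transplant or steroids can shift z-scores and no drug effect can be inferred without a control.

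The cost is some SAP text, a small extra derivation including the chart rule, and a few more tables. The inputs are already collected. The visit grid of Table 6-1 could not be read in the text available, so the visits at which height and head circumference are taken should be confirmed when the tables are specified; this is not a fault in the plan.
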